The last non-missing measurement prior to start of study medication will serve as the Baseline measurement. Measurements performed on the day of first intake of study medication are assumed to be “prior to start of study medication”, as long as it has not been confirmed that the procedure was performed afterwards. This assumption is justified as following the sequence of procedures as specified in the study protocol. The intake of study medication should be the last procedure on the Visit day.

The MRI scans will be reconciled during central MRI review process. Therefore, MRIs will be considered as Baseline MRIs if assigned to the Baseline Visit by the central imaging review.

Definition of Study Periods

- Baseline Period: The Baseline Period is defined as the Period between the Screening and the Baseline MRI scan.
- Post-Baseline Period: The post-Baseline Periods that are used in the primary analysis are defined as follows:
 - Period 1 (p₁) is defined as the Period between Month 1 and Month 6 MRI scans.
 - Period 2 (p₂) is defined as the Period between Month 2 and Month 6 MRI scans
 - Period 3 (p₃) is defined as the Period between Month 3 and Month 6 MRI scans

In addition, the following post-Baseline Periods are defined solely for tertiary analyses:

Three months Periods

- Period 3.1 (p_{3.1}) is defined as the Period between Baseline and Month 3 MRI scans.

Six months Periods

- Period 6.1 (p_{6.1}) is defined as the Period between Baseline and Month 6 MRI scans,
- Period 6.2 (p_{6.2}) is defined as the Period between Month 6 to Month 12 MRI scans,
- Period 6.3 (p_{6.3}) is defined as the Period between Month 12 to Month 18 MRI scans,
- Period 6.4 (p_{6.4}) is defined as the Period between Month 18 to Month 24 MRI scans.

Periods excluding the Period between the Baseline scan and the Month 1 MRI scan:

- Period 11.1 (p_{11.1}) is defined as the Period between Month 1 to Month 12 MRI scans,
- Period 11.2 (p_{11.2}) is defined as the Period between Month 1 to Month 24 MRI scans.

Yearly Periods:

- Period 12.1 (p_{12.1}) is defined as the Period between Baseline to Month 12 MRI scans,
- Period 12.2 (p_{12.2}) is defined as the Period between Month 12 to Month 24 MRI scans.

2 -Year Period:

- Period 24.1 (p_{24.1}) is defined as the Period between Baseline to Month 24 MRI scans.

Sequential Visit Periods

- Period 100.0 (p_{100.0}) is defined as the Period between Screening and Baseline (equivalent to Baseline Period) MRI scans

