Note: the number of new or enlarging T2 (with and without T1 Gd+) will be provided by central reading for each of the Periods including the Sequential Visit Periods, except for Period 3.1. For Period 3.1, the sum of the Sequential Visit Periods 100.1, 100.2 and 100.3 will be calculated.

For the calculation of the CUA lesion count, only T2 lesions that did not emerge from a T1 Gd+ lesion will be taken into account.

- Total active T2 lesion count (without T1 Gd+) =
Total new T2 lesion count without T1 Gd+
+ Total enlarging T2 lesion count without T1 Gd+

and will be standardized to the length of the Period (i.e. annualized). Total active T2 lesion count (without T1 Gd+) will only be calculated if T1 Gd+ counts for beginning and end of the corresponding Period are non-missing.

CUA lesion count

The number of CUA lesions for a Period will be defined as the sum of the T1 Gd+ and new or enlarging T2 counts for the respective Period and will be standardized to one scan (for T1) or one year (for T2) to harmonize the units of the 2 assessments.

$\#CUA(p_{\text{post-Baseline}})$ = Annualized CUA lesion count (by post-Baseline Period per 1 year)
= Mean T1 Gd+ lesion count (by Period i)
+ Annualized total active T2 lesion count (without T1 Gd+)
(by Period i per 1 year) Different from the primary analysis, T2

lesion count will be standardized to 1 year instead of 1 month due to longer periods and for comparison with other studies,

The CUA lesion count will only be calculated if both components (T1 and T2) are non-missing.

Data Handling in case of major PDs

PDs will not be considered in the planned statistical analyses (i.e., all data will be analyzed independent from any reported PD) except for PD due to MRI taken during steroid treatment (MRI will be excluded from the primary analysis).

Covariates and stratification factors

Age

Age (years) at time of Informed Consent (loaded from iRT). Missing age will be replaced as follows if used as a covariate:

- Age will be estimated from the year of birth (year of IC – year of birth), as recorded in the electronic Case Report Form (eCRF),
- If year of birth is missing, age will be imputed by the mean age of the FAS.

EDSS at Baseline

Expanded Disability Status Scale (EDSS) at Baseline will be categorized by:

- ≤ 3 (reference),
- >3 .

Missing EDSS at Baseline will be imputed by the median Baseline EDSS of the FAS if used as a stratification factor.

Pooled centers

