The increase will be defined as sustained when it occurs on two post-Baseline Visits, which are at least 166 days (6 months × 30 - 14 days Visit Window) apart and no observations at any other Visit (including unscheduled Visits) in between are less than the defined increase.

The occurrence of a 6MCDP is defined as:

- Yes: sustained increase in EDSS score that started during the Treatment Period,
- No: at least 2 post-Baseline EDSS assessments that are 166 (or more) days apart are available and no sustained EDSS progression that started during the Treatment Period,
- Unknown: Otherwise.

Start date of the 6MCDP is the start date of the first sustained increase in EDSS.

MRI activity:

- Yes: At least one T1 Gd+ at any scan assigned to Month 6, Month 12, Month 18, Month 24 Visit, or at least one active T2 during any of the following Periods: Baseline to Month 6, Month 6 - Month 12, Month 12 - Month 18, Month 18 – Month 24 Visits.
- No: T1 Gd+ = 0 at all scans assigned to Month 6, Month 12, Month 18, Month 24 Visit that have a value and at least one T1 Gd+ value from Month 18 or Month 24 Visit available, and all active T2 = 0 during any of the following Periods: Baseline - Month 6, Month 6 - Month 12, Month 12 - Month 18, Month 18 - Month 24 Visits that have a value and at least one active T2 value from periods Month 12 - Month 18 or Month 18 - Month 24 Visits available.
- Unknown: Otherwise.

CCI [REDACTED]

[REDACTED]

[REDACTED]

[REDACTED]

CCI [REDACTED]

CCI [REDACTED]

Brain Atrophy

- Yes: Annualized percentage brain volume change during the Treatment Period < -0.4% (see Section 14.3.11),
- No: Annualized percentage brain volume change during the Treatment Period ≥ -0.4%,
- Unknown: Otherwise.

Analysis of NEDA

NEDA and its components will be analyzed with a logistic regression with adjusting factors age (in years) and EDSS at Baseline (≤3, >3).

Analysis (Analysis Set)	Derivation	Statistical Analysis Methods	Missing data handling
Tertiary endpoint: NEDA at 24 months			
Tertiary (FAS)	NEDA-3 during Treatment Period	Logistic regression: Adjusting factors: 
 • Age (in years), • EDSS at Baseline (≤3, >3). Estimated probability and corresponding Standard Errors (SE) will be presented including 2-sided p-values and 95% CIs.	Unknown status: Subjects with an unknown status will be excluded from the logistic regression. Missing covariate or stratification information will be imputed as specified in Section 9.

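### NEDA MRI activity (standard definition): a missed Month 6 or Month 12 scan can yield No activity against a positive longer T2 read; a missed Month 18 scan yields Unknown

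*SAP*

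**What the plan says.** SAP 14.3.12 gives the standard definition of MRI activity, which has a T1 Gd+ part and a T2 part.

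- *Yes*: any T1 Gd+ lesion at Month 6, 12, 18 or 24, or "at least one active T2 during any of the following Periods: Baseline to Month 6, Month 6 - Month 12", Month 12-18 or Month 18-24.
- *No*, T1 part: "T1 Gd+ = 0 at all scans assigned to Month 6, Month 12, Month 18, Month 24 Visit that have a value", with at least one value from Month 18 or 24.
- *No*, T2 part: zero in the four windows "that have a value and at least one active T2 value from periods Month 12 - Month 18 or Month 18 - Month 24".
- *Unknown*: anything else. Unknown subjects are left out of the logistic regression.

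SAP Section 9 ties each Period to two named scans. For example, Period 6.2 "is defined as the Period between Month 6 to Month 12 MRI scans". It also defines longer Periods: 12.1 "is defined as the Period between Baseline to Month 12 MRI scans", 12.2 "is defined as the Period between Month 12 to Month 24 MRI scans" and 24.1 "is defined as the Period between Baseline to Month 24 MRI scans", plus 11.1 (Month 1-12) and 11.2 (Month 1-24). For the tertiary MRI data, "the number of new or enlarging T2 (with and without T1 Gd+) will be provided by central reading for each of the Periods"; only Period 3.1 is obtained by summing. So the longer comparisons are read in their own right. Section 9 also says that missing data are not replaced unless a section states otherwise. The visible text of 14.3.12 states nothing of the kind for MRI activity.

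**The concern.** A 6-month window needs a scan at each end, so one missing scan usually removes two adjacent windows. The *No* rule skips windows without a value and requires only one late T2 window. A subject can therefore be certified free of MRI activity with half or more of the 24 months of T2 change unread at 6-month resolution. Meanwhile the database may hold a central read across that gap showing new lesions.

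Two other parts of the SAP sit badly with this. NEDA-3 is meant to describe the entire Treatment Period. And 14.3.7 analyses active T2 for Periods 12.1, 12.2 and 24.1, so the same subject can show active T2 in one table and no MRI activity in another. By contrast, brain atrophy, the other MRI component of NEDA-4, has a stated fallback in 14.3.11 when the Month 24 comparison is missing.

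In a single-arm trial the estimated NEDA probability is itself the result. There is no control arm in which the same error would occur and partly cancel.

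**Working it through.** **1. The rule by missing scan.** Assume all available 6-month T2 windows and all available Gd+ counts are zero, and Month 1 is present.

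| Missing scan | Windows lost | Rule gives | Longer reads spanning the gap |
|---|---|---|---|
| Month 6 | Baseline-6, 6-12 | *No* | 12.1, 24.1, 11.1, 11.2 |
| Month 12 | 6-12, 12-18 | *No* | 24.1, 11.2 |
| Months 6 and 12 | Baseline-6, 6-12, 12-18 | *No*, on 18-24 alone | 24.1, 11.2 |
| Month 18 | 12-18, 18-24 | *Unknown* | 12.2, 24.1, 11.2 |
| Month 24 | 18-24 | *No* | none |

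Periods 11.1 and 11.2 start at Month 1, so they can show activity but cannot clear the first month. The Sequential Visit Periods do not help, because none spans a missing Month 6, 12 or 18 scan.

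**2. Exposure.** The documents give no missing-scan rate and no figure to reproduce. Assume each scan is missing independently with probability q.

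P(Month 6 or 12 missing) = 1 - (1 - q)²

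- q = 5%: 1 - 0.95² = 9.75%
- q = 10%: 1 - 0.90² = 19%

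Enumerating all patterns of the five scans (Baseline, 6, 12, 18, 24), and also counting a missing Baseline bridged by 11.1 or 11.2, 13.3% and 23.5% of subjects could be *No* with an unused longer read over a lost window. That is 35 and 62 of the planned 265. At most a further 4.8% and 9.2% (13 and 24 of 265) could be *Unknown* with such a read.

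**3. From exposure to misclassification.** A wrong *No* also needs a positive longer read, no Gd+ at the remaining scans, and zero T2 in the remaining windows. Let a₁ be the chance of active T2 in Baseline-6, a the chance in each later window, and g the chance that such a lesion still enhances at the scan ending its window. All three are assumptions, with windows treated as independent.

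- Only Month 6 missing: [(1 - a·g) - (1 - a₁)(1 - a)] × (1 - a)²
- Only Month 12 missing: (1 - a₁) × [(1 - a·g) - (1 - a)²] × (1 - a)
- Each pattern has probability q(1 - q)⁴.

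Low case (q = 5%, a₁ = 0.2, a = 0.1, g = 0.4):
- Month 6: (0.96 - 0.72) × 0.81 = 0.194
- Month 12: 0.8 × (0.96 - 0.81) × 0.9 = 0.108
- Sum 0.302 × 0.0407 = 1.2% of subjects

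High case (q = 10%, a₁ = 0.5, a = 0.1, g = 0.2):
- Month 6: (0.98 - 0.45) × 0.81 = 0.429
- Month 12: 0.5 × (0.98 - 0.81) × 0.9 = 0.077
- Sum 0.506 × 0.0656 = 3.3% of subjects

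The same calculation over every missing-scan pattern, using reads 12.1, 12.2 and 24.1, gives 1.3% and 4.0%, or about 4 and 11 of 265. For NEDA-3 it is lower still, because the subject must also have no qualifying relapse and no confirmed disability progression.

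**The case against.** - **Gd+ also counts.** A reader might infer that MRI activity rests on four T2 windows alone. It does not: any T1 Gd+ at Month 6, 12, 18 or 24 gives *Yes*. This stands and narrows the point to subjects without visible enhancement. It does not close the gap, since a lesion formed between scans need not still enhance at the next one.
- **10-19% is not an error rate.** A reader might take it as inflation of the NEDA rate. It is the share of subjects exposed, at an assumed missing rate.
- **Only intermittent gaps matter.** Subjects who leave early and lack the late windows become *Unknown*, not falsely *No*. Faulty scans are repeated (protocol 7.3.1.2.1), and early-termination assessments are mapped to the nearest visit with a missing assessment (SAP Section 9). This limits the size, not the mechanism.
- **Unseen sources.** The lesion-counting charter and the data transfer specification may substitute a neighbouring scan. If so, the gap would close, but the SAP defines Periods by named scans and mentions no substitution.
- **Redaction.** Parallel analyses use a frequent-MRI version whose definition is not visible, so extending the criticism to it would be unsupported.
- **Overcorrection.** Letting any overlapping read override four complete zero windows would redefine the endpoint, since one discordant 24-month comparison would then decide the code. This is right, and the fix is limited accordingly.
- **Low stakes.** NEDA is tertiary and exploratory, the longer T2 reads are reported separately, and NEDA components are listed by subject. This bears on priority. It does not make the coding correct.

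**Conclusion.** The point holds for the standard definition. As written, a subject missing Month 6 or Month 12, with no Gd+ at the available scans and zero T2 in the remaining windows, is coded *No* even when a longer central read over the gap is positive. This error runs only toward disease-free and carries into NEDA-3, NEDA-4 and NEPAD. Separately, a clean subject missing only Month 18 is coded *Unknown* and dropped from the regression despite an available 12.2 or 24.1 read.

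At an assumed 5-10% missing per scan, 10-19% of subjects miss Month 6 or 12. Under the further assumptions shown, about 1-4% of all subjects would be misclassified on MRI activity. Both ranges move with the assumptions; the direction does not.

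The documents do not support saying that every missing scan produces a false *No*: Month 18 gives *Unknown*, and Month 24 alone has no longer read to contradict it. The primary endpoint is unaffected. This should be corrected, but it does not threaten the trial's main conclusion.

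**What to change.** In SAP 14.3.12, add a rule to the T2 part of standard MRI activity that applies only where one of the four 6-month windows is missing:

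- Use the available centrally read Period or Periods that span the missing window (11.1, 11.2, 12.1, 12.2, 24.1).
- *Yes* if any such read has an active T2 count of at least 1.
- *No* only if the available 6-month windows and the bridging reads are all zero and together cover Baseline to at least Month 18.
- *Unknown* otherwise, unless activity is shown elsewhere.

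Leave three things unchanged: subjects with all four windows read, the T1 Gd+ part, and the Section 9 exclusion of later efficacy data for a Delayed Treatment Course 2. If the central reading rules already substitute a neighbouring scan, say so in 14.3.12.

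The cost is SAP wording and derivation code, with no new reads. The NEDA rate may be slightly lower. Some subjects with gaps that no read covers will move from *No* to *Unknown*, while some now *Unknown* after a missed Month 18 scan will become classifiable.

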- End = Start of study medication at or after the Month 12 Visit - 1 day, or if the subject did not receive Treatment Course 2: Start of study medication of Treatment Course 1 + 457 days (which is obtained by 360 (12 months) + 90 (3 months) + 7 (Visit window)) or date of discontinuation, if earlier.

Course 2 Treatment Period:

- Start = Start of study medication at or after the Month 12 Visit,
- End = End of Treatment Period.

Definition of Delayed Treatment Course 2

The Treatment Course 2 will be defined as delayed, if the start of study medication is delayed by more than 3 months (= 90 days) or did not start at all i.e.:

- Start of Study medication of Treatment Course 2 > Start of Study Medication of Treatment Course 1 + 457 days (which is obtained by 360 (12 months) + 90 (3 months) + 7 (Visit window)), or
- Treatment Course 2 never started (i.e., no study medication taken at or after the Month 12 Visit).

Data handling in case of a Delayed Treatment Course 2

For subjects with a Delayed Treatment Course 2, only data observed during the Course 1 Treatment Period will be analyzed in all efficacy analyses. Efficacy data after the Course 1 Treatment Period will be counted as missing in the statistical analyses and marked in the listings. In all efficacy analyses defined by Period, the subject will be classified as if the subject discontinued at the end of the Course 1 Treatment Period. For subjects without a delay the whole Treatment Period will be analyzed.

For all other analyses (except efficacy) the data is not limited to the Course 1 Treatment Period for subjects with a Delayed Treatment Course 2.

Definition of start of COVID-19-Pandemic

The start of COVID-19 pandemic will be defined by country as the earliest date of either the date of the first death from COVID-19 occurred in each country according to the published data by European Centre for Disease Prevention and Control on 26th June 2020 (<https://www.ecdc.europa.eu/en/publications-data/download-todays-datageographic-distribution-covid-19-cases-worldwide>) or 11th March 2020 (when the WHO declared COVID-19 pandemic).

Visit timing with respect to COVID-19 pandemic

A Visit is defined to be performed after the start of COVID-19 pandemic if the Visit end date is greater than the start of COVID-19 pandemic date.

Conversion factors

The following conversion factors will be used to convert days into months or years for all observations except Visit related dates:

- 1 month = 30.4375 days,

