14.3.12 No Evidence of Disease activity

No Evidence of Disease activity (NEDA), also referred to as freedom from disease activity, is a new goal that is emerging in MS treatment. NEDA is a composite measure of disease activity, including relapses, cognition and disability progression, and MRI activity. Since MRI activity is a broad concept, which can correspond to the MRI lesion load or changes in brain volume monitoring brain atrophy, the distinction between NEDA-3 and NEDA-4 will be provided.

NEDA-3

NEDA-3 at Month 24 is defined by the absence of:

- Qualifying Relapses,
- 6-months Confirmed Disability Progression (6MCDP),
- MRI activity,

during the whole Treatment Period. If the information for one of the components is unknown, and none of the other components are observed, NEDA-3 will be classified as “unknown”. Thus, NEDA-3 can be derived from its components as follows:

- Yes: all components = “No”,
- No: at least one of the components =” Yes”,
- Unknown: Otherwise.

NEDA-3 (frequent MRI)

NEDA-3 at Month 24 is defined by the absence of:

- Qualifying Relapses,
- 6-months Confirmed Disability Progression (6MCDP),
- MRI activity (frequent MRI),

during the whole Treatment Period. If the information for one of the components is unknown, and none of the other components are observed, NEDA-3 will be classified as “unknown”. Thus, NEDA-3 can be derived from its components as follows:

- Yes: all components = “No”,
- No: at least one of the components =” Yes”,
- Unknown: Otherwise.

NEDA-4

NEDA-4 at 24 Month is defined as the composite endpoint of NEDA-3 and the absence of brain atrophy.

NEDA-4 (frequent MRI)

NEDA-4 (frequent MRI) at Month 24 is defined by the composite endpoint of NEDA-3 (frequent MRI) and the absence of brain atrophy.

Qualifying Relapse

- Yes: qualifying relapses reported during the Treatment Period,
- No: study completed, and no qualifying relapse reported during Treatment Period,
- Unknown: otherwise.

6-Months Confirmed Disability Progression (6MCDP)

A Sustained Increase in EDSS score, is defined by an increase of:

- at least 1.5 points if the Baseline EDSS score was 0, or
- at least 1 point if Baseline EDSS score was between 0.5 and 4.5 inclusively, or
- at least 0.5 point if the Baseline EDSS score was at least 5,

that occurs over a 6-month time Period.

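### NEDA and NEPAD keep early leavers who had an event but exclude event-free leavers, so inclusion in the 24-month estimate depends on the outcome

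*SAP*

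**What the plan says.** SAP 14.3.12 builds NEDA-3 from three components: qualifying relapse, 6-month confirmed disability progression (6MCDP) and MRI activity.

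- **Failure.** NEDA-3 is No when "at least one of the components" has occurred. Completion is not required. The relapse component works the same way: "Yes: qualifying relapses reported during the Treatment Period".
- **Success.** Every component must be No. For relapse the rule is "No: study completed, and no qualifying relapse reported during Treatment Period", so a relapse-free early leaver cannot reach No on that component.
- **Neither.** "If the information for one of the components is unknown, and none of the other components are observed, NEDA-3 will be classified as" Unknown.
- **Analysis.** "Subjects with an unknown status will be excluded from the logistic regression". The reported result is a model-based figure: "Estimated probability and corresponding Standard Errors (SE) will be presented including 2-sided p-values and 95% CIs".

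NEDA-4 is NEDA-3 plus absence of brain atrophy. NEPAD (SAP 14.3.13) is NEDA-3 plus further progression components, with the same missing-data handling. Both inherit the rule.

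SAP Section 9 sets efficacy data after the Course 1 Treatment Period to missing when Course 2 starts more than 3 months late or never starts. In analyses by Period "the subject will be classified as if the subject discontinued at the end of the Course 1 Treatment Period". For a late starter that period ends the day before Course 2 begins. If Course 2 is never received, it ends at Course 1 start + 457 days, or at discontinuation if earlier.

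**The concern.** Take two subjects who leave at Month 10. One had a qualifying relapse at Month 4 and stays in the regression as a failure. The other had no event and is removed. Early leavers can therefore enter only as failures. Protocol 5.5.1 supplies one such route: a subject who relapses and starts another DMD stops trial assessments, and counts as a failure if the relapse qualifies.

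The Course 2 rule extends the pattern to people still attending. MRI activity can be No only with a late T1 Gd+ value (Month 18 or 24) and a late active-T2 value (Month 12–18 or 18–24). Once those values are set to missing, an event-free subject becomes Unknown, while one with an earlier event stays as No.

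In a single-arm trial the estimated probability and its interval are the NEDA result, and no control arm shares the selection. The SAP already allows for unequal follow-up in the relapse rate (SAP 14.3.18, offset for treatment-period length). The visible text has no equivalent for NEDA or NEPAD.

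**Working it through.** The documents state no NEDA rate, dropout rate or NEDA sample-size figure, so there is no planned figure to reproduce. Everything below is a range over assumptions, except the planned N of about 265 (Protocol synopsis).

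**Inputs.** p = true 24-month NEDA probability (assumed 0.20–0.60). d = share leaving early, unrelated to later activity (assumed 5–20%). q = share of leavers with an event before leaving.

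**Formula.** Subjects kept are all completers (1−d) and leavers with an event (d·q). Successes are p(1−d). So

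SAP rate = p(1−d) / [(1−d) + d·q]

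- Constant hazard, leaving times uniform over 24 months: q = 1 − (1−p)/(−ln p).
- Extreme case, all events precede leaving: q = 1 − p.

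**Example.** p = 0.40, d = 0.20: q = 1 − 0.60/0.916 = 0.345. Rate = 0.32/(0.80 + 0.20 × 0.345) = 0.368, which is 3.2 points low.

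**Bias in percentage points, constant hazard (in brackets: all events precede leaving)**

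| True p | d = 5% | d = 10% | d = 15% | d = 20% |
|---|---|---|---|---|
| 0.20 | −0.5 (−0.8) | −1.1 (−1.6) | −1.6 (−2.5) | −2.2 (−3.3) |
| 0.40 | −0.7 (−1.2) | −1.5 (−2.5) | −2.3 (−3.8) | −3.2 (−5.2) |
| 0.50 | −0.7 (−1.3) | −1.5 (−2.6) | −2.3 (−4.1) | −3.3 (−5.6) |
| 0.60 | −0.7 (−1.2) | −1.4 (−2.6) | −2.2 (−4.0) | −3.1 (−5.5) |

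**Simulation** (N = 265, 4,000 runs per setting). For p = 0.40 the SAP rule averages 0.385 at d = 10% and 0.368 at d = 20%; Kaplan-Meier on the same data gives 0.400 both times. With half the cumulative hazard in the first 6 months, the SAP rule gives 0.383 and 0.363. The sampling SD is about 3 points, so the bias is about half a standard error at 10% loss and one at 20%.

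**Never-started Course 2, cut at about Month 15.** Take p = 0.50 and 10% of subjects truncated. The share with an event by Month 15 is 1 − 0.5^(15/24) = 0.352. Rate = 0.45/(0.90 + 0.10 × 0.352) = 0.481, about 2 points low.

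**When the sign changes.** Let completers have rate 0.40, d = 10%, and let c be the chance that an excluded subject would have stayed event-free to Month 24. The true rate is 0.90 × 0.40 + 0.10 × 0.655 × c = 0.36 + 0.0655c, against an SAP rate of 0.385.

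| c | True rate | Bias (points) |
|---|---|---|
| 0.60 | 0.399 | −1.4 |
| 0.385 | 0.385 | 0 |
| 0.20 | 0.373 | +1.2 |
| 0 | 0.360 | +2.5 |

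Non-informative leaving corresponds to c = 0.61. In this example about 17 of 265 subjects are Unknown (0.0655 × 265). The all-No and all-Yes bounds are 0.360 and 0.426 (0.36 + 0.0655).

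**The case against.** The strongest reply is that the direction is not fixed. A reader might infer from the rule that the reported rate must be too low. The documents do not support that. Subjects who never receive Course 2 have half the planned treatment and may do worse later; the last table shows the bias vanishing and then reversing. Other rules in the same section push upward: a completer with missing scans is still MRI No if every available value is zero and one late T1 and one late T2 value exist, and for 6MCDP the rule is "No: at least 2 post-Baseline EDSS assessments that are 166 (or more) days apart are available". Events can be missed under either rule, so the net sign is open. This objection stands.

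A reader might also add the early-leaving and Course 2 effects together. SAP Section 9 counts a never-started Course 2 as delayed, so anyone leaving before Month 12 is in both groups; the sum double-counts. Nor is there support for large truncated shares: Protocol 8.5.1 expects substantial delay in only a small number of subjects. The Month 15 cut does not describe late starters, whose data run to the day before Course 2.

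Part of a remedy is already planned. SAP Section 14 promises descriptive summaries for all efficacy endpoints, Section 9 keeps missing values in the denominator as a separate category, and the NEDA components are listed by subject. If Unknown is tabulated that way, the bounds are simple arithmetic. But the descriptive percentage itself equals the all-No bound (0.36 at 10% loss and 0.32 at 20% for true 0.40), so it is not a less biased estimate.

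Logistic regression for categorical endpoints is prespecified in Protocol 8.5.3, and Kaplan-Meier also assumes non-informative censoring. Both are fair points. They argue for keeping the logistic model alongside the addition and for showing bounds. Some nearby SAP text is redacted, so a further NEDA analysis cannot be ruled out.

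**Conclusion.** The outcome-dependent inclusion follows directly from the definitions and applies to NEDA-3, NEDA-4 and NEPAD, including event-free subjects with a delayed or never-started Course 2. Under non-informative leaving the estimate is too low by about 0.5 to 3.3 points for 5–20% loss, true NEDA of 0.20–0.60 and constant hazard. If all events precede leaving, the shortfall at 20% loss is 3.3 to 5.6 points. These figures rest on assumed rates, and the leaving and truncation effects should not be summed. With a worse outlook among the excluded, the bias shrinks or reverses.

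A reader might take this as a threat to the trial's main result. It is not: NEDA and NEPAD are tertiary and exploratory, and the CUA analysis does not use them. The change is still worth making, because the published percentage would otherwise carry an avoidable selection effect that its confidence interval does not reflect.

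**What to change.** In SAP 14.3.12 and 14.3.13:

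1. Add an estimate of the 24-month NEDA and NEPAD proportions from time to first component failure (Kaplan-Meier or discrete visit intervals). Censor event-free subjects at their last complete assessment, within the Course 1 Treatment Period where the Section 9 truncation applies.
2. Report the number Unknown beside each logistic estimate, with bounds that set all Unknown to Yes and all to No. The bounds cover informative leaving.
3. Keep the logistic model as supportive.

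The cost is one additional analysis on data already collected. Its limits should be stated. Failure times are known only to the visit interval. Six-month confirmation restricts ascertainment of late progression. Brain atrophy in NEDA-4 is a single end-of-period classification and needs a convention for its failure time. Kaplan-Meier itself assumes non-informative censoring, which is why the bounds belong beside it.
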